7.9 Safety

Safety will be assessed by recording adverse events (AEs) and serious adverse events (SAEs). Details of definitions of AEs and SAEs are outlined in the study protocol.

Descriptive statistics of AEs and SAEs will be presented by treatment arm on the ITT population. The following figures will be included overall; separately for child, primary carer and co-parent and by type (Appendix Table 10):

- The total number of AEs;
- The number and percentage of participants reporting at least 1 AE;
- The number and percentage of participants reporting a treatment related AE;
- The total number of SAEs;
- The number and percentage of participants reporting at least 1 SAE;
- The number and percentage of participants reporting a treatment related SAE;
- The number and percentage of participants reporting each severity and frequency of SAE.

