7.5 Analysis Populations

7.5.1 Intention to treat (ITT)

To avoid any potential bias in the analysis, the primary outcome analysis will be conducted on the ITT population unless otherwise stated. Participants will be analysed according to the treatment arm they were randomised to and analysis will include all participants with outcome data.

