	xx	xx.x(xx.x)	xx	xx.x(xx.x)	xx	xx.x(xx.x-xx.x)	0.xxxx
	xx	xx.x(xx.x)	xx	xx.x(xx.x)	xx	xx.x(xx.x-xx.x)	
	xx	xx.x(xx.x)	xx	xx.x(xx.x)	xx	xx.x(xx.x-xx.x)	
	xx	xx.x(xx.x)	xx	xx.x(xx.x)	xx	xx.x(xx.x-xx.x)	0.xxxx

* p-value from interaction test

vi. Safety analysis results

Table 10: Summary of safety data

	Intervention	Control	All
Number (%) of participants who experienced ≥ 1 AE	xx(xx.x%)	xx(xx.x%)	xx(xx.x%)
Number of all AEs (including repeated events)	xx	xx	xx
AE related to intervention			
Unlikely	xx(xx.x%)	xx(xx.x%)	xx(xx.x%)
Unrelated	xx(xx.x%)	xx(xx.x%)	xx(xx.x%)
	Intervention	Control	All
Number (%) of participants who experienced ≥ 1 SAE	xx(xx.x%)	xx(xx.x%)	xx(xx.x%)
Number of all SAEs (including repeated events)	xx	xx	xx
SAE related to intervention			
Unrelated	xx(xx.x%)	xx(xx.x%)	xx(xx.x%)
Intensity of SAE			
Mild	xx(xx.x%)	xx(xx.x%)	xx(xx.x%)
Moderate	xx(xx.x%)	xx(xx.x%)	xx(xx.x%)
Severe	xx(xx.x%)	xx(xx.x%)	xx(xx.x%)
Frequency of SAE			
Isolated	xx(xx.x%)	xx(xx.x%)	xx(xx.x%)
Intermittent	xx(xx.x%)	xx(xx.x%)	xx(xx.x%)
Unknown	xx(xx.x%)	xx(xx.x%)	xx(xx.x%)

vii. Adherence to intervention

Table 11: Summary of the number of sessions received by participants

Programme	Consent			Number of sessions						
				1	2	3	5	8**	10	12
IY-I	Xx	Attended at least this many sessions	n	xx	xx	xx	xx	xx	xx	xx
			(%)	xx%	xx%	xx%	xx%	xx%	xx%	xx%
IY-T	xx	Attended at least this many sessions	n	xx	xx	xx	xx	xx	xx	xx
			(%)	xx%	xx%	xx%	xx%	xx%	xx%	xx%

Table 12: Summary of IY-I and IY-T groups

	Number assigned to a group	Number who attended one or more sessions	Median sessions attended (IQR)	Min, Max.
IY-I	xx	xx(xx%)	xx(xx,xx)	x,xx
IY-T	xx	xx(xx%)	xx(xx,xx)	x,xx

Table 13: Summary of all intervention sessions

	Number of Sessions that occurred	Median (IQR)	Min, Max.
IY-I	xx	xx(xx,xx)	x,xx
IY-T	xx	xx(xx,xx)	x,xx

Table 14: Summary of breastfeeding at baseline

Variable		Intervention	Control	All
		(n=xxx)	(n=xxx)	(n=xxx)
Breastfeeding History	Never breastfed	xx(xx.x%)	xx(xx.x%)	xx(xx.x%)
	Previously breastfed, now stopped	xx(xx.x%)	xx(xx.x%)	xx(xx.x%)
	Currently breastfeeding -	xx(xx.x%)	xx(xx.x%)	xx(xx.x%)
	Not Known ¹	xx(xx.x%)	xx(xx.x%)	xx(xx.x%)
Of those currently breastfeeding	Does not use bottle	xx(xx.x%)	xx(xx.x%)	xx(xx.x%)
	Also uses bottle	xx(xx.x%)	xx(xx.x%)	xx(xx.x%)
Childs age when stopped breastfeeding (weeks)	N (%)	xx(xx.x%)	xx(xx.x%)	xx(xx.x%)
	Mean (SD)	xx.x (xx.x)	xx.x (xx.x)	xx.x (xx.x)
	Median (IQR)	xx.x(xx,xx)	xx.x(xx,xx)	xx.x(xx,xx)

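### Safety is summarised on an ITT population described as participants with outcome data, so recorded events in families who gave no follow-up data could fall out of the table

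*SAP*

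**What the plan says.** Section 7.9 of the SAP sets the safety population: "Descriptive statistics of AEs and SAEs will be presented by treatment arm on the ITT population". It asks for the figures overall, by type, and separately for child, primary carer and co-parent, and refers to Appendix A, Table 10.

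The term ITT is described only in section 7.5.1. That section opens with the primary outcome, stating that "the primary outcome analysis will be conducted on the ITT population unless otherwise stated", and then says: "Participants will be analysed according to the treatment arm they were randomised to and analysis will include all participants with outcome data". The only other heading under analysis populations is per protocol (7.5.2), which is descriptive. The SAP defines neither a safety set nor an all-randomised set.

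On relatedness, section 7.9 lists among its required figures "The number and percentage of participants reporting a treatment related AE" and "The number and percentage of participants reporting a treatment related SAE". In Table 10, the block headed "AE related to intervention" has two rows, Unlikely and Unrelated. The block headed "SAE related to intervention" has one row, Unrelated.

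**The concern.** The description in 7.5.1 suits an analysis of questionnaire scores, where a participant without a score cannot contribute. It does not suit adverse events, which can be recorded whether or not a questionnaire comes back. By naming the ITT population, section 7.9 carries the outcome-data condition into the safety table. A family could be randomised, have an event recorded, withdraw before FU1 and then not be counted.

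The people at risk of exclusion are those who left soonest, and withdrawal after an event is a case that a safety summary should keep. If early loss also differs between arms, the descriptive comparison of arms is affected as well.

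The timing matters too. Section 11 has unblinded data delivered after database freeze, partly so that analysis sets can be defined. If 7.9 is left unclear, the safety denominator may be settled by someone who can see the allocation.

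**Working it through.** The SAP states no safety figure to reproduce, so the check is mainly a reading of sections against each other. A small illustration of size follows.

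**Step 1: what outcome data means.**
- Section 4.1: baseline measures are collected before randomisation.
- Section 7.6.1: baseline ASQ:SE-2 and baseline PHQ-9 enter the primary model as covariates, and the modelled outcome is the follow-up score.
- If baseline scores counted as outcome data, every randomised family would qualify and the condition in 7.5.1 would exclude no one. The natural reading is therefore follow-up data.

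**Step 2: who is left out on that reading.**
- Out: families with no follow-up data at all. Section 7.2.1 and Table 3 expect some losses before FU1, because they count discontinuations in that interval.
- In: any family that gave FU1 data and left later.
- In, as a rule: anyone offered IY-I, because section 4.2 bases that offer on the FU1 scores.

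**Step 3: co-parents.** Section 7.9 wants co-parent events reported separately. Section 2.1 says that co-parents are not asked to complete the ASQ:SE-2. The condition in 7.5.1 therefore does not settle which co-parents form the denominator.

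**Step 4: size.** From the SAP summary table, 606 participants are allocated 5:1:
- intervention: 606 × 5/6 = 505
- control: 606 × 1/6 = 101

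The rest is assumed, because the SAP gives neither attrition nor event rates. Let *d* be the share with no follow-up data, *r_S* the risk of at least one event in stayers, and *r_L* the risk in leavers.

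- Rate on all randomised = (1 − d) × r_S + d × r_L
- Rate on the restricted set = r_S
- Understatement = d × (r_L − r_S)
- Share of affected participants lost = d × r_L / [(1 − d) × r_S + d × r_L]

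With r_S = 5% and r_L = 15%:

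| d | Families left out (intervention / control) | All-randomised rate | Tabulated rate | Understatement (points) | Affected participants lost |
|---|---|---|---|---|---|
| 2% | 10 / 2 | 5.2% | 5.0% | 0.2 | 6% |
| 5% | 25 / 5 | 5.5% | 5.0% | 0.5 | 14% |
| 10% | 50 / 10 | 6.0% | 5.0% | 1.0 | 25% |
| 20% | 101 / 20 | 7.0% | 5.0% | 2.0 | 43% |

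Example at d = 10%: 0.90 × 5% + 0.10 × 15% = 6.0%, and the share lost is 1.5 / 6.0 = 25%.

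With r_S = r_L = 5%, the rate is 5.0% on either set, but a share *d* of affected participants (2% to 20%) still disappears from the count.

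**Step 5: Table 10 against section 7.9.** The text requires related AEs and related SAEs. The shell has no row for either. This is a mismatch between text and shell and has no bearing on who is in the population.

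**The case against.** The strongest reply is that no exclusion is stated. Section 7.5.1 describes who contributes to the primary outcome analysis and does not say that events are discarded when questionnaires are missing. The SAP also uses the term outcome measures for baseline scores (section 7.3 and Table 1), and baseline data precede randomisation. On that usage every randomised family has outcome data and nobody is lost.

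Part of this stands: the wording is ambiguous. But the reply leaves the condition in 7.5.1 with no function and does not fit the primary model. It also leaves the safety denominator open to two readings, and one sentence would close it.

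Three stronger readings are tempting, and the SAP does not support them.

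- *That harms in all families who left early are lost.* Only families with no follow-up data are affected. In the intervention arm these would ordinarily have had at most the book, because the group programmes are offered on follow-up scores. Events during or after the groups are not normally lost by this route.
- *That event percentages would shift by several points.* The shift is d × (r_L − r_S). A 3-point shift needs a risk difference of 3 / 0.05 = 60 points at 5% loss, or 3 / 0.20 = 15 points at 20% loss. At equal risk there is no shift.
- *That the plan can only report unrelated events.* Section 7.9 expressly requires related ones, and a dummy table does not override the text. Other shells are also unfinished: the subgroups in Table 9 are still to be confirmed although section 10.1 lists them. The full relatedness scale may be in the protocol, to which 7.9 refers for AE and SAE definitions.

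**Conclusion.** The point holds in limited form. Section 7.9 applies to safety a population described for the primary outcome and limited to participants with outcome data, and the SAP offers no other set. On the natural reading, families without any follow-up data leave the safety table together with any recorded events.

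The size cannot be known from the SAP. Under the assumed risks of 5% and 15% and 2% to 20% loss before FU1, the percentage would be understated by 0.2 to 2.0 points. The percentage is understated only if those leavers have more events than stayers. The event count falls whenever any of them had an event.

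The conclusion rests on reading outcome data as follow-up data. If the sponsor meant all randomised families, the wording should say so. The missing rows in Table 10 are a separate, clerical matter and add nothing to the size of this one.

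**What to change.** In section 7.9, replace the reference to the ITT population with a statement that AEs and SAEs are summarised on all randomised participants, with their child and co-parent, by allocated arm, whether or not outcome data were returned.

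As a separate minor alignment, add to Table 10 the related categories that 7.9 already requires, for both AEs and SAEs, using whatever relatedness scale the trial records.

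The cost is one sentence and a few table rows. No new data are needed and no efficacy analysis changes. The edit should be made before unblinded data are released to define analysis sets.

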7.10 Changes from analysis specified in the Protocol

Section 10 of protocol version 10 says “Evaluating the overall effectiveness of the proportionate delivery of IY will be assessed using a multilevel mixed model to allow for a treatment and time effect whilst allowing for the clustering by participant and group treatments and confounding and stratifying variables”. As discussed in section 7.6.1 we will no longer account for treatment level clustering and will account for repeated measurements using a marginal model fitted using GEE.

Section 10 of protocol version 10 says “ITT analysis will be conducted at the cluster level using summary measures” as well as “the individual level with test statistics adjusted for intra-cluster correlation”. Because participants can get IY-I alone, IY-T alone or both, there is no way of grouping participants into clusters that remain stable throughout the intervention.

Sex of primary caregiver will no longer be used as a covariate due to the finding from the pilot that there were too few male primary caregivers for the associated model parameter to be estimated.

Section 10 of protocol version 10 says the ITT analysis will include “predictors of missing values”. This has been operationalised in this SAP by undertaking sensitivity analysis of the primary ITT using multiple imputation as described in section 8.1.1.

8 Detailed Statistical Methods and Calculations

8.1 Missing Spurious & Unused Data

8.1.1 Missing data

The primary outcome will be analysed using observed data with imputation for item non-response (see Table 2 in Section 9.2) but no imputation for missing survey data, and we will assess the amount and patterns of missing data and test the sensitivity of estimates of treatment effects using the multiple imputation by chained equation (MICE) technique (Buuren and Groothuis-Oudshoorn, 2011) implemented in STATA for those variables where a logistic regression model shows them to be significant predictors of missing-ness. In addition to all variables in the primary analysis including treatment group, which will all be included the MI, we will consider the following variables:

- Age of primary caregiver;
- Eligibility for IY-I
- Eligibility for IY-T

Treatment effects and their 95% CIs will be presented in a forest plot alongside those produced using the primary analysis methods (section 7.6).

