4.2 Inclusion in the Intervention arm

If a participant is allocated to the intervention arm, they receive the IY-I Book. Following the first follow up (2 months post baseline), only participants with a Parent PHQ-9 score ≥ 5 OR Child ASQ:SE2 score \geq 'Monitoring' in the intervention arm are offered the IY-I programme. Following the second follow up (9 months post baseline) only participants with Parent PHQ-9

³ In protocol v10 the CARE Index is described as a child attachment measure and listed as a child secondary outcome. Child attachment is just one part of the Index and we will use the overall dyadic synchrony score which is a parent-child dyad measure.

score ≥ 5 OR Child ASQ:SE2 score \geq 'Monitoring' in the intervention arm are offered the IY-T programme.

Non-research participants may be included in the IY-I and IY-T groups. Parents can be invited by service staff to join the group based on professional judgement/assessment that they meet the same eligibility criteria as research participants. We do not collect data for these participants; they attend as they would for any other parenting intervention delivered at that site. This is accepted practice in these types of research interventions when there are concerns about group size.

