7.6 Analysis of the primary outcome

7.6.1 Primary Analysis of the primary outcome

The ASQ:SE-2 is a set of questionnaires with different versions for different age groups. Consequently, different versions will be completed at each time point. The primary analysis will use raw ASQ:SE-2 scores as the scoring is the same across treatment arms and estimates will be easier to interpret. For ASQ:SE-2 either the 2 month or the 6 month questionnaire is administered at Follow-up 1 dependent upon the developmental age of the baby. If we observe an imbalance between arms in the number receiving the 2 months and 6 months versions we will adjust the score for those receiving the 2 months version by multiplying by 1.24. We have based the adjustment on the monitoring thresholds (25 and 30 for the 2 and 6 months surveys) and referral thresholds (35 and 45 for the 2 and 6 months surveys). The adjustment is midway between those required to preserve the monitoring threshold (30/25) and the referral threshold (45/35). If participants have completed both questionnaires, we will use the 6 months version and exclude them from the potential adjustment procedure.

The overall treatment effect will be estimated using a marginal model fitted using general estimating equations to account for the repeated measures with a Gaussian family, identity link, robust standard errors and an autoregressive covariance structure of order 1 AR(1). If the model does not converge using AR (1) we will use an unstructured correlation structure. The fixed effects will be stratifying variables (baseline ASQ:SE-2 score, baseline PHQ-9 score,

site⁴ and sex of child); potential confounders (ethnicity of the primary caregiver, marital status and highest level of education and follow up time (using an indicator variable for each time point)).

- The therapist induced clustering effect will not be fitted because the offer of IY-I and IY-T is conditional on outcome at FU1 and FU2 so clustering is confounded with treatment effect leading to biased estimation of the latter.
- The repeated measurements will be accounted for using a marginal model fitted using GEE because accounting for repeated measures using a mixed model inflates the type 1 error (random intercept only model) or gives a biased estimate of the treatment effect (random intercept and slope model).

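### SAP section 8.1.1 screens the extra imputation variables on a p-value for missingness and omits continuous follow-up PHQ-9, a limited weakness in the plan's only missing-data sensitivity analysis

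*SAP*

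**What the plan says.** Under SAP section 8.1.1 the primary analysis uses observed data, with no imputation of missing questionnaires. Sensitivity to missing data is then tested by chained-equation multiple imputation (MI) "for those variables where a logistic regression model shows them to be significant predictors of missing-ness". The same section fixes what is always in the model: "In addition to all variables in the primary analysis including treatment group, which will all be included the MI". Three further variables are to be considered: "Age of primary caregiver", "Eligibility for IY-I" and "Eligibility for IY-T".

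Section 7.6.1 shows what enters without a screen. "The fixed effects will be stratifying variables (baseline ASQ:SE-2 score, baseline PHQ-9 score" begins the list, which goes on to site, child sex, ethnicity, marital status, education and time.

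Section 4.2 defines eligibility for each group programme by a PHQ-9 of 5 or more, or an ASQ:SE-2 in the Monitoring zone or above, at FU1 for IY-I and at FU2 for IY-T. Table 1 shows PHQ-9 collected at baseline and all three follow-ups.

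Section 7.6.2 names one missing-data sensitivity analysis, this one. Section 7.10 says the protocol's commitment on predictors of missing values is "operationalised in this SAP by undertaking sensitivity analysis of the primary ITT using multiple imputation".

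**The concern.** An auxiliary variable helps an imputation through its relation to the missing outcome, and helps most when it is related to missingness as well. The screen in section 8.1.1 looks only at missingness, and only through a significance test. A variable can fail that test because the test lacks power, and failing it does not show that the variable can safely be left out. Section 8.1.1 also does not say which visit's missingness is modelled, or whether candidates are tested singly or jointly.

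The candidate list adds a second weakness. Parental depression is a plausible driver of both dropout and the parent-reported ASQ:SE-2, and it is measured at every visit. Yet follow-up PHQ-9 can enter only as one half of an either/or flag cut at a threshold. FU3 PHQ-9 has no route in.

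At stake is how much the single check on missing data can detect. Group programmes are offered in the intervention arm only, so dropout that depends on need differently by arm is conceivable. That is the case in which the choice of auxiliaries matters for the treatment effect.

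**Working it through.** **Inputs from the SAP.** 606 participants at 5:1 (summary table), so 606 × 5/6 = 505 intervention and 606/6 = 101 control. Tests are two-sided at 5% (section 7.1); no separate level is given for the screen. The SAP gives no missingness rate, no odds ratio (OR) and no retention probability for the screen, so there is no plan figure to reproduce. Missingness rates, ORs and flag prevalences below are assumptions.

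**Step 1: chance that the screen keeps a modest true predictor.** With missing fraction m and predictor variance v:

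SE(log OR) = 1/√(N·m·(1−m)·v); power ≈ Φ(log OR/SE − 1.96).

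At m = 0.25, 606 × 0.25 × 0.75 = 113.6.

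- Age, OR 1.2 per SD, v = 1: SE = 1/√113.6 = 0.094; log 1.2 = 0.182; power 0.49.
- Flag with 30% prevalence, OR 1.5, v = 0.3 × 0.7 = 0.21: SE = 1/√(113.6 × 0.21) = 0.205; log 1.5 = 0.405; power 0.51.

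Holding these ORs and moving m from 15% to 35% gives power from 36% to 59%.

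**Step 2: vary the OR as well.** Percentage of times a true binary predictor is dropped (1 − power, two-proportion test, N = 606):

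| Prevalence | Missing | OR 1.25 | OR 1.5 | OR 2.0 | OR 3.0 |
|---|---|---|---|---|---|
| 50% | 5% | 91 | 81 | 56 | 22 |
| 50% | 10% | 87 | 68 | 30 | 3 |
| 50% | 20% | 81 | 49 | 8 | <1 |
| 50% | 30% | 76 | 38 | 3 | <1 |
| 30% | 20% | 82 | 52 | 10 | <1 |

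For age with OR 1.2, 1.3 or 1.5 per SD, the drop rate is 73%, 51% or 15% at 10% missing, and 57%, 27% or 2% at 20% missing.

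The flags are unknown for anyone who missed the visit that defines them, so 606 is generous for them. With 485 (606 × 0.8 = 484.8), a 30%-prevalence flag at 20% missing is dropped 60% of the time at OR 1.5 and 17% at OR 2.

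**Step 3: effect on the treatment estimate (illustration).** 3,000 runs per setting, 505:101, about 20% missing at one visit, true effect zero. The outcome is 0.4 × earlier ASQ + b × follow-up PHQ-9 + residual with SD 0.85, where the two predictors have unit variance and correlation 0.3. With b = 0.3 the outcome variance is 0.16 + 0.09 + 2 × 0.4 × 0.3 × 0.3 + 0.7225 = 1.04, so the units are close to one outcome SD. Dropout depends on follow-up PHQ-9. Imputation is by regression within arm, always using earlier ASQ. Caregiver age was not simulated. Mean bias:

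| Dropout log OR per SD, intervention / control | b | No auxiliary | Eligibility if significant | Eligibility always | Continuous PHQ-9 |
|---|---|---|---|---|---|
| 0.3 / 0.3 | 0.3 | −0.001 | −0.001 | −0.001 | −0.002 |
| 0.5 / 0.5 | 0.3 | −0.001 | 0.000 | 0.000 | 0.000 |
| 0.3 / 0 | 0.3 | −0.016 | −0.014 | −0.010 | 0.000 |
| 0.5 / 0 | 0.3 | −0.027 | −0.019 | −0.016 | 0.001 |
| 0.8 / 0 | 0.3 | −0.042 | −0.028 | −0.027 | −0.001 |
| 0.5 / 0 | 0.5 | −0.046 | −0.032 | −0.028 | 0.000 |

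The empirical SE is about 0.11 throughout. At log OR 0.5 in the intervention arm only:

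- Bias left by the planned rule: 0.019/0.11 = 17% and 0.032/0.11 = 29% of one SE.
- Part due to the screen: 0.019 − 0.016 = 0.003 and 0.032 − 0.028 = 0.004.
- Part that remains even with eligibility always in: 0.016 and 0.028. Continuous PHQ-9 removes it.

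**The case against.** The strongest reply is that the screen touches very little. Every primary-model variable and treatment arm go in unscreened, so the imputation already draws on the child's other ASQ:SE-2 scores, baseline ASQ:SE-2 and baseline PHQ-9. Only three extras are at risk, and the primary estimate, interval and p-value do not change. This stands, and it sets the size of the point.

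Three stronger readings are tempting, and the SAP does not support them.

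- A reader might infer that the MI must agree with the primary result by construction. It need not: imputing from the unscreened variables uses information on dropout differently from an observed-data GEE, so the two can differ even if all three extras are dropped.
- A reader might infer that follow-up PHQ-9 is ignored. FU1 and FU2 PHQ-9 are present in dichotomised form within the eligibility flags. What is missing is the continuous score.
- A reader might infer that the screen loses true predictors half the time in general. That holds for modest predictors only; strong predictors of dropout are usually kept once missingness reaches 20%.

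It is also fair to say that FU3 PHQ-9 is collected at the same visit as the FU3 outcome, so it will often be missing with it and add little. And putting both flags and continuous scores into chained equations as free variables would let imputed flags contradict imputed scores. Both points bear on the remedy and are met there.

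**Conclusion.** The point holds as a modest improvement to a sensitivity analysis. Section 8.1.1 selects auxiliaries by a criterion that ignores their relation to the outcome, and it leaves out the continuous form of a measure collected at every visit. The omission matters more than the screen.

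The drop rate has no single value. With N = 606 and a two-sided 5% test, it runs from under 1% to about 91% for a binary predictor over ORs of 1.25 to 3 and missingness of 5% to 30%.

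The bias figures rest on the simulated model and on dropout that depends on follow-up PHQ-9 in the intervention arm only. With weaker dependence (log OR 0.3) the planned rule left 0.014. If dropout depends on PHQ-9 equally in both arms, bias is about zero under every option, and the choice hardly affects the treatment effect.

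**What to change.** In section 8.1.1, replace the significance screen with a fixed imputation model: all primary-model variables and arm, as now, plus caregiver age and continuous primary-carer PHQ-9 at FU1 and FU2, whatever their p-values. FU3 PHQ-9 can be added where observed. Derive the IY-I and IY-T eligibility flags passively from the imputed PHQ-9 and ASQ:SE-2 scores, or leave them out as redundant. Keep the logistic regression for missingness as description only.

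The cost is a short change of text and a slightly larger imputation model in an analysis that is already planned. Fixing the list in advance also removes the need to define the screen.
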